6.20.5 Power and Sample Size

Based upon our recent trial data, we assume high level mupirocin resistance in 0.07 of MRSA isolates at baseline. We estimate collection of 2,400 isolates (600 per arm in the each of the intervention and baseline periods). As in UH3 Aim 1, power is based on a post-only comparison of 1200 subjects, 24 per hospital. Assuming intracluster correlation of 0.001, we will have 80% power to detect 0.12 high level mupirocin resistance in the decolonization arm, assuming that resistance remains at 0.07 in the usual care arm.

For both MRSA and gram negative bacteria, we will calculate the proportion of isolates resistant to chlorhexidine. If the proportion of MRSA that is resistant is truly as large as 0.1%, we will have at least a 90% probability of detecting ≥ 1 resistant strain among 2400 isolates, 70% among the 1200 post-period isolates, and 45% among 600 isolates in the post period in the intervention arm. If the resistance rate increases to 0.5%, we have a 95% chance of observing at least one case in the 600 intervention isolates from the follow-up period.

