In a previous trial, we used the logistic regression analogue to proportional hazards regression models and simulation to estimate power.²¹⁰ Now, however, we propose an interesting and, to our knowledge, novel approach to power calculation, which we dub “bootstrap power calculation.” This method is described below and in an article published since the trial was planned.²¹⁵ Briefly, the bootstrap is a powerful technique that uses the observed sample to approximate the underlying population, rather than a convenient analytic distribution.²¹⁶ The bootstrap power approach relies on the fact that we possess a large quantity of baseline data already. Loosely put, we (1) bootstrap a sample of observations from our observed baseline data to serve as the baseline sample in the power calculations. Then we (2) bootstrap another sample from the baseline data to serve as the intervention period data. Next, (3) we implement the randomization scheme in the bootstrapped sample. Then (4), for a randomly selected subset of the outcomes (e.g., bloodstream infections) observed in the bootstrapped intervention period sample in the hospitals randomized to intervention, we artificially change the outcome from infection to no infection. This represents the effect of the intervention, which we control by changing the size of the subset selected for this change. Simultaneously (5), for this subset we change the date of the event from the date of infection to the date of discharge, transfer to a non-eligible unit, or death—i.e., the date of censoring, had no infection been observed. Finally (6), we fit the planned frailty model described in **Section 6.10.11** above and record whether the null hypothesis of no association was rejected or not. This process is repeated many times, and the proportion of rejections is an estimate of the power under the given effect size. A confidence limit on this estimated power can be generated. In the table below, we show the power for removing the outcome from 0, 10, 20, and 30% of the subjects in the intervention arm in the intervention period. Removing 0% of the outcomes is a test of the technique: since we are not reducing the infection rate, the null is true, and rejections should occur only about 5% of the time.

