6.20.4 Analysis

For mupirocin and chlorhexidine separately, we will report the proportion of resistant isolates in each arm in the baseline and intervention periods. We will test differences between arms in resistance by fitting a generalized linear mixed logistic regression model with arm, baseline vs. intervention period, and their interaction as predictors. The interaction term assesses whether the difference in the probability of resistance between the baseline and intervention periods is significantly different between arms.

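### The 80% power stated for mupirocin resistance belongs to an intervention-period comparison; the planned arm-by-period interaction test has about 50%

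*Protocol*

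**What the plan says.** Protocol section 6.20.4 will test arm differences in resistance by "fitting a generalized linear mixed logistic regression model with arm, baseline vs. intervention period, and their interaction as predictors". It names the interaction as the term that shows whether the change from baseline to intervention differs between arms.

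Section 6.20.5 gives the power. The inputs are 600 isolates per arm in each period, and then: "we assume high level mupirocin resistance in 0.07 of MRSA isolates at baseline"; "Assuming intracluster correlation of 0.001"; "assuming that resistance remains at 0.07 in the usual care arm". The claim is: "we will have 80% power to detect 0.12 high level mupirocin resistance in the decolonization arm". The comparison behind it is stated openly: "As in UH3 Aim 1, power is based on a post-only comparison of 1200 subjects, 24 per hospital".

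For Aim 1, section 6.10.12 describes a bootstrap that resamples both a baseline and an intervention period. In its last step, "we fit the planned frailty model described in" section 6.10.11, which is the model whose interaction term decides trial success.

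The SAP lists emergence of resistance in Table 1, but its power section (2.3) has nothing on it.

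**The concern.** The power figure and the planned test concern different contrasts. The figure compares 600 with 600 isolates in the intervention period. The interaction subtracts the baseline difference between arms from that comparison, so it adds the sampling error of another 600 plus 600 isolates. Differencing pays off only when it removes substantial between-hospital variation, and at an intracluster correlation of 0.001 there is almost none to remove.

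Resistance to the two agents is one of the three specific aims of the intervention phase, and section 4.1 (Element #4) names it as a potential harm. For a harm endpoint, overstated power matters most when the result is null: a non-significant interaction could be taken as reassurance from an 80%-powered analysis.

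**Working it through.** **Inputs** (section 6.20.5 unless noted)

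- Isolates per arm and period: 600, in four cells, 2,400 in total
- Cluster size in the intervention period: 24 per hospital, so 1,200/24 = 50 hospitals
- Resistance: 0.07 in both arms at baseline and in usual care afterwards; 0.12 in the decolonization arm afterwards
- Intracluster correlation 0.001, giving a design effect of 1 + 23 × 0.001 = 1.023
- Significance level: not given in 6.20.5. I assume two-sided 0.05, the level in section 6.10.11 for Aim 1.

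**Common quantities**

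- Log odds ratio, 0.12 against 0.07: ln[(0.12/0.88)/(0.07/0.93)] = ln(1.812) = 0.594
- Variance of one cell's log odds at 0.07: 1/(600 × 0.07 × 0.93) = 0.0256
- The same at 0.12: 1/(600 × 0.12 × 0.88) = 0.0158

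**Step 1: reproduce the stated 80%**

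- Variance, intervention period only: 0.0256 + 0.0158 = 0.0414. With the design effect, 0.0423, so SE = 0.206.
- Power = Φ(0.594/0.206 − 1.96) = 82%.

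On the proportion scale, with an effective 600/1.023 = 586.5 isolates per arm, the pooled normal formula gives 83%, a t reference with 48 degrees of freedom 82%, and the continuity-corrected formula 81%. The stated figure is therefore right for the contrast it describes.

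**Step 2: the planned interaction**

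- Variance: 3 × 0.0256 + 0.0158 = 0.0926, so SE = 0.304. This is 0.0926/0.0414 = 2.24 times the intervention-period variance.
- Power = Φ(0.594/0.304 − 1.96) = Φ(−0.007) = 49.7%.
- With the design effect of 1.023 applied to every cell, 48.8%.

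A simulation of 20,000 trials (50 hospitals, 24 isolates per hospital and period, a hospital random intercept matching the 0.001 correlation, Wald tests) gave 49.8% for the interaction and 83.9% for the intervention-period comparison.

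**Step 3: what the interaction can detect with 80% power**

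- At 0.15 in the decolonization arm the log odds ratio is 0.852. Variance with the design effect is 1.023 × [0.0768 + 1/(600 × 0.15 × 0.85)] = 0.0919, SE = 0.303, power = Φ(0.852/0.303 − 1.96) = 80%.
- To keep 0.12 as the target: (1.96 + 0.842)² × [3/0.0651 + 1/0.1056]/0.594² ≈ 1,235 isolates per cell, or about 1,263 after the design effect. That is roughly 5,050 isolates against the planned 2,400.

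**Step 4: would a larger intracluster correlation rescue the claim?**

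No. Even if hospital effects were perfectly stable across periods, so that differencing removed them fully, interaction power stays at 50% to 52% for correlations from 0.001 to 0.05. Meanwhile the intervention-period power falls. At 0.05 the design effect is 1 + 23 × 0.05 = 2.15, SE = √(0.0414 × 2.15) = 0.298, and power is Φ(0.594/0.298 − 1.96) = 51%.

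**The case against.** **No calculation is wrong, and the basis is disclosed.** Both are true. Section 6.20.5 says plainly which comparison it uses, and 80% is a fair figure for it. But it gives no power for the test in 6.20.4, and no reason for powering a different one.

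**The 50% rests on choices the protocol leaves open.** This stands in part; each alternative raises the figure, but none to 80%.

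- One-sided 0.05, since Aim 2 is worded as increased resistance: Φ(1.953 − 1.645) = 62%.
- A risk-difference contrast, if the wording of 6.20.4 on probabilities is taken literally: about 60%. The planned model is logistic.
- More isolates. The count is an estimate, section 5.30.4 asks for 12 months of baseline collection against nine in 6.20.2, and 6.20.6 allows longer collection. Assuming the nine-month yield of 600 scales to 12 and 21 months (about 800 and 1,400 per arm), power is about 71%. Section 6.20.6 offers the extension as a remedy for shortfall, not as a plan for more isolates.

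**It is a secondary matter.** Protocol Table 10 places resistance among the outcomes for secondary manuscripts. Power for the primary outcome is unaffected, and 6.20.4 promises the proportions by arm and period, so readers will see more than a p-value. All of this stands. It limits the reach of the problem but does not correct the figure.

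**The interaction is deliberate.** It is the trial's chosen way of handling residual baseline imbalance (sections 6.10.4 and 6.10.11), so replacing it for one aim is a design choice. That is fair, and restating the power is enough on its own.

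**Conclusion.** The concern holds. Under the protocol's own inputs the planned logistic interaction has 49% to 50% power for 0.12 against 0.07, not 80%, and reaches 80% only at about 0.15. This assumes two-sided 0.05 and 600 isolates in each of the four cells. The more favourable readings give 60% to 71%, all short of the claim.

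The fault is a mismatch between power calculation and test, not an arithmetic slip. The statement that Aim 1 was powered in the same way no longer matches section 6.10.12, which was updated in June 2015.

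**What to change.** Choose one of two changes in section 6.20.5, and add the matching text to the SAP, which has none for Aim 2.

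- **(a) Keep the interaction and restate the power.** About 50% for 0.12, or 80% for about 0.15, with the significance level and sidedness given.
- **(b) Make the test match the power.** Prespecify in 6.20.4 an arm comparison in the intervention period, with each hospital's baseline resistance as a covariate or with the arms constrained equal at baseline, as randomization justifies. A simulation of the constrained version under the protocol's inputs gave about 83%. This relies on the correlation of 0.001: by the Step 1 formula, the unadjusted intervention-period comparison has 75% at 0.01 and 68% at 0.02, so a short sensitivity range should accompany the figure.

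Under either option, delete the statement that Aim 1 used the same basis. The cost is about a paragraph of wording and no extra isolates; under (a) the stated figure becomes less favourable. Table 15 schedules the resistance analysis for year 4, so the change can precede it.

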We will create a PowerPoint presentation for an introductory webinar to participating laboratories at the beginning of strain collection. This presentation will introduce laboratory staff to study staff and detail the entire process for de-identified strain collection. This will be followed by mailed laboratory toolkits (see example from prior trial, **Appendix E**), which will include 1) a Step-by-Step instruction sheet, 2) a Frequently Asked Questions (FAQ) sheet, 3) collection log sheets with a clipboard, 4) de-identified study ID labels, 5) FedEx mailing instruction sheets, 6) a shipment packing list, 7) a shipping schedule, and 8) a quick reference wall chart with a streamlined diagram of key elements for collection (see example from prior trial, **Appendix F**).

In order to ensure that the volume of MRSA+ and gram-negative rod (GNR) isolates that are collected during the baseline period are sufficient to support analysis around whether or not study agents engendered resistance, it will be crucial to obtain a full 12-months worth of isolates. It is anticipated that participating ABATE Infection Study hospital laboratories will begin collecting and banking isolates that fit study criteria beginning 3/01/2013 and continue collection through 2/28/2014 in order to support this activity. Collected isolates will include MRSA+ and the following eight select GNR organisms. Isolates will have already been collected as part of a patient's routine medical care.

E. coli	P. aeruginosa
K. pneumoniae, K. oxytoca	A. baumannii
P. mirabilis	S. maltophilia
S. marcescens	Burkholderia spp.

Once full IRB approval is obtained (either via ceding to the HPHC IRB or pursuing individual review) at each participating hospital during the baseline year (see Section 5.20.0), isolates may then be shipped to the central study laboratory at Rush University, Chicago for analysis and storage.

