6.20.2 Strain Collection

Strain collection will include MRSA and other pathogens since chlorhexidine targets a broad range of microbes and rare cases of resistance have been reported in select gram-negative bacteria, namely acinetobacter, burkholderia, E coli, klebsiella, proteus, pseudomonas, serratia, and stentrophomonas.^{218 219 220} Study staff will coordinate with each clinical microbiology laboratory director for the collection of MRSA and these gram negative bacteria for a 9-month period toward the end of both the baseline and intervention periods for each arm. A total of 2,400 MRSA and 2,800 gram negative bacteria will be collected.

Trial staff will provide each microbiology laboratory with a toolkit with detailed instructions about strain collection, including the list of pathogens, participating units, and time window for collection. Microbiology technologists will be instructed to target strains with a collection date at least 2 days after admission based upon unit location and admission date, which are available during usual specimen processing. Similar to our prior trial, the toolkit will include a Step-by-Step instruction guide, a Frequently Asked Questions (FAQ) sheet, FedEx mailing instruction sheet, deidentified study ID labels, collection log sheets with clipboard, shipment packing list, and shipping schedule (see example from prior trial, **Appendix E, G**). In addition, a quick reference wall cling will be sent that provides a streamlined diagram of the key elements for collection (see example from prior trial, **Appendix F**). Details will be reviewed in laboratory-specific coaching calls.

Chocolate agar slants and shipping kits (STP-250MD, Saf-T-Pak Inc.) will be sent to each laboratory on a regular basis for monthly batch shipment of strains. Initially, trial staff will contact laboratory liaisons once weekly until processes are in place. Trial staff will contact each laboratory prior to each anticipated shipment.

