All bacterial isolates will have susceptibility to chlorhexidine determined by a microtiter method using 20% aqueous chlorhexidine digluconate (Sigma-Aldrich LLC, St. Louis, MO) diluted in broth medium appropriate for the microbe tested.²¹⁸ Since national standards do not yet exist for chlorhexidine resistance, we will define resistance as a minimum inhibitory concentration (MIC) of chlorhexidine that is outside of the reported wildtype distribution for each microbial species. Based upon recent literature, we will use a resistance breakpoint of ≥ 8 mcg/ml for MRSA,¹⁷ ≥ 32 mcg/ml for klebsiella, pseudomonas, and serratia,²¹⁶⁻²¹⁷ and ≥ 64 mcg/ml for burkholderia, proteus, and stenotrophomonas.²¹⁵⁻²¹⁷ These species were chosen because of their relatively high chlorhexidine MICs compared to other bacterial species and/or their association with outbreaks linked to contaminated commercial chlorhexidine products (burkholderia). In addition to assessing MIC breakpoints, we will evaluate the proportion of strains with a high MIC within the susceptible range between baseline and intervention strains. Decreased susceptibility to chlorhexidine has been associated with the presence of various multidrug efflux pumps.^{223 224 225} If chlorhexidine resistant (or nearly resistant) isolates are identified, we will use polymerase chain reaction methods to evaluate isolates for the presence of efflux pump genes. If efflux pump genes are found, additional characterization of resistance may be done including assays to quantify expression of efflux pumps and to measure the effect of inhibition of efflux on chlorhexidine MICs.

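### The chlorhexidine-resistance model for gram-negative isolates has no species term, so a shift in species mix that differs between arms could pass for a change in resistance

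*Protocol*

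**What the plan says.** **Collection.** Protocol Section 6.20.2 names eight gram-negative groups: "acinetobacter, burkholderia, E coli, klebsiella, proteus, pseudomonas, serratia, and stentrophomonas". Section 5.30.4 gives a matching set: "Collected isolates will include MRSA+ and the following eight select GNR organisms", and its list includes E. coli and A. baumannii. Section 6.20.2 plans 2,800 gram-negative isolates and 2,400 MRSA.

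**Testing and definition.** Section 6.20.3 says "All bacterial isolates will have susceptibility to chlorhexidine determined by a microtiter method". It gives a general rule: "we will define resistance as a minimum inhibitory concentration (MIC) of chlorhexidine that is outside of the reported wildtype distribution for each microbial species". It then lists numeric breakpoints: 8 mcg/ml for MRSA; 32 mcg/ml for klebsiella, pseudomonas and serratia; 64 mcg/ml for burkholderia, proteus and stenotrophomonas. E. coli and Acinetobacter have no number. The section explains its list with "These species were chosen because of their relatively high chlorhexidine MICs compared to other bacterial species", and gives outbreaks traced to contaminated product as a further or alternative reason. It also plans to compare, between periods, the share of strains with high MICs that still fall in the susceptible range.

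**Analysis.** Section 6.20.4 reports the proportion resistant by arm and period, and tests it "by fitting a generalized linear mixed logistic regression model with arm, baseline vs. intervention period, and their interaction as predictors". It separates mupirocin from chlorhexidine but does not say whether MRSA and gram-negatives are modelled apart. Section 6.20.5 adds: "For both MRSA and gram negative bacteria, we will calculate the proportion of isolates resistant to chlorhexidine".

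**SAP.** Table 1 lists emergence of resistance as a secondary outcome. The SAP gives no separate method for it, and the covariates listed for adjusted models in Section 2.2 do not include species.

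**The concern.** Resistance is the whole of Aim 2, and Section 4.1 of the protocol names it as the potential harm to be compared between arms. Aim 2 is judged by the arm-by-period interaction.

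A pooled proportion is an average of species-specific proportions weighted by how often each species was cultured. It can move because resistance moved within species or because the weights moved, and a model with only arm, period and interaction cannot tell these apart.

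A shift that differs by arm is plausible. The intervention acts on the flora being sampled, Section 6.0.2 hypothesises fewer gram-negative resistant organisms and urinary infections under decolonization, and Section 6.20.6 allows that isolate yield may fall. Nothing says that every species would fall in proportion. The error could go either way: a false signal of resistance, or a real one masked.

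**Working it through.** **1. The plan's own figures.** Section 6.20.5 gives the chance of seeing at least one resistant isolate, which is 1 − (1 − p)^n:

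- p = 0.1%, n = 2,400: 0.909 (stated: at least 90%)
- p = 0.1%, n = 1,200: 0.699 (stated: 70%)
- p = 0.1%, n = 600: 0.451 (stated: 45%)
- p = 0.5%, n = 600: 0.951 (stated: 95%)

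All reproduce. The 0.1% figures are stated for MRSA, and the sample sizes are those of the MRSA collection. No chlorhexidine power or detection figure is given for gram-negatives.

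**2. Cut-offs.** Three groups at 32 mcg/ml plus three at 64 mcg/ml make six of eight. The two without a number are E. coli and Acinetobacter.

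**3. Effect of a shift in mix.** The inputs below are assumptions, because the documents give no species mix and no gram-negative resistance rates:

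- 2,800 isolates split evenly over two arms and two periods: 2,800 / 4 = 700 per cell.
- Two classes of species with resistance a (higher) and b (lower), constant throughout. The higher class is 30% of isolates in three cells; in the decolonization arm's intervention period its share rises by 5, 10 or 20 points.
- Pooled proportion P = w·a + (1 − w)·b, where w is the share of the higher class.
- Three cells share the same P, so the interaction odds ratio is [P₁/(1 − P₁)] / [P₀/(1 − P₀)].
- The rejection probability is from a Wald test with variance equal to the sum over four cells of 1/[700·P(1 − P)], ignoring clustering by hospital.

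Example, a = 10%, b = 1%, shift 10 points: P₀ = 0.3 × 0.10 + 0.7 × 0.01 = 0.037; P₁ = 0.4 × 0.10 + 0.6 × 0.01 = 0.046; odds ratio = (0.046/0.954) / (0.037/0.963) = 1.25. Expected resistant isolates go from 25.9 to 32.2 per 700.

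| Resistance a / b | Shift (points) | P₀ → P₁ | Interaction OR | Rejection at nominal 5% |
|---|---|---|---|---|
| 2% / 0.5% | 5 | 0.95% → 1.025% | 1.08 | 5.1% |
| 2% / 0.5% | 10 | 0.95% → 1.10% | 1.16 | 5.4% |
| 2% / 0.5% | 20 | 0.95% → 1.25% | 1.32 | 6.6% |
| 10% / 1% | 5 | 3.7% → 4.15% | 1.13 | 6.1% |
| 10% / 1% | 10 | 3.7% → 4.6% | 1.25 | 8.9% |
| 10% / 1% | 20 | 3.7% → 5.5% | 1.51 | 19.1% |
| 30% / 2% | 5 | 10.4% → 11.8% | 1.15 | 9.0% |
| 30% / 2% | 10 | 10.4% → 13.2% | 1.31 | 20.1% |
| 30% / 2% | 20 | 10.4% → 16.0% | 1.64 | 54.8% |

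**4. When nothing happens.** If both arms start from the same mix and shift equally, the interaction odds ratio is 1.00. If a = b, it is 1.00 whatever the shift. Within species it is 1.00 in every row, which is what a species-stratified analysis targets.

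**The case against.** **Pooling is not declared.** The sentence on gram-negatives sits in a power section, and neither 6.20.4 nor 6.20.5 says that all species go into one model. That stands. But no by-species analysis is stated anywhere, so one proportion is the natural reading.

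**Different cut-offs are not a fault.** Agreed. Species-specific definitions are what give a resistant/susceptible split its meaning. The gap is the absence of species from the model.

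**The two groups without a number.** A reader might infer that E. coli and Acinetobacter can enter only the denominator, as never resistant, so that resistance in them would be invisible and the pooled proportion understated by their share. The documents do not support this. The general rule in Section 6.20.3 covers every species, and its high-MIC comparison would also include them. What is missing is a number fixed in advance, which leaves room to set it after results are seen. The list may also mean that the two groups were deliberately left out of the breakpoint analysis, but the plan does not say that they leave the denominator.

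**Any shift in mix biases the test.** A reader might infer this too. It is too strong: the shift must differ between arms, and species must differ in resistance prevalence. Resistant-organism and urinary-infection outcomes measure burden, not mix, so they make a differential shift plausible but do not show one.

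**Resistance is expected to be rare.** Section 6.20.2 describes gram-negative resistance as rare, and Section 6.20.1 reports one chlorhexidine-resistant isolate among 4,321 MRSA in the earlier trial. At 0.5%, a rate used in Section 6.20.5, a cell of 700 would hold 3.5 resistant isolates. At such rates the test's error rate hardly moves. This limits the size of the problem.

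**Conclusion.** The point holds in a limited form. As written, the analysis implies a single gram-negative proportion tested without species, and so cannot separate composition from emergence of resistance when the mix shifts differently by arm and species differ in prevalence. Under the assumed inputs the spurious odds ratio runs from 1.08 to 1.64. The rejection rate stays between 5.1% and 6.6% when resistance is 2% or less, and reaches 54.8% only with strong contrasts (30% against 2%) and a 20-point shift in one arm. These figures rest on an even split of 2,800 isolates, an assumed starting share of 30%, and no allowance for clustering.

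The missing numbers for E. coli and Acinetobacter are a gap in specification; they do not show that the two groups would be misclassified. The primary outcome and the detection and mupirocin figures in Section 6.20.5 are unaffected. The change is worth making because it serves a named aim and needs no new data.

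**What to change.** **Section 6.20.4.** State that gram-negatives are analysed separately from MRSA. Add species as a stratum or model term: a random intercept, or a conditional, exact or penalised method if events are sparse, since fixed species effects with few events risk separation. Report resistance by species, arm and period, and draw no conclusion from the unadjusted pooled proportion.

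**Section 6.20.3.** Before arm-level data are seen, either state the wild-type-based cut-offs for E. coli and Acinetobacter under the existing rule, or exclude both groups from the breakpoint denominator and say so.

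**Cost.** This is wording and analysis only, because Section 6.20.3 already confirms identification and measures MICs. Estimates for rare species will be imprecise. Exclusion would also shrink the sample: if the two groups were 30% to 60% of isolates (assumed), 2,800 × 0.70 = 1,960 down to 2,800 × 0.40 = 1,120 would remain, or 490 down to 280 per arm and period.
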